## 2. OBJECTIVES

The primary objective of this Registry is:

- To determine the long-term safety of anti-HCV regimens in the pediatric population as determined by assessments of growth and development.

The secondary objectives of this Registry are:

- To determine whether subsequent detection of HCV RNA in subjects who relapse following sustained virologic response (SVR) represents the re-emergence of pre-existing virus, the development of resistance mutations, or whether it is due to re-infection;
- To characterize resistance mutations and the persistence of resistance mutations in pediatric subjects who did not achieve SVR;

The exploratory objective of this Registry is:

P  
P

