### 8.2. Primary Safety Endpoints

The primary safety endpoints are:

- Growth data by visit grouped by age and gender;
- Development by Tanner Pubertal Stage Assessment;

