#### **8.6.3.2. Growth Data**

For each subject, body height, body weight, and Z-scores at baseline and at each visit will be calculated based on sex and age.

The changes in body height and weight measurements for all subjects will be examined to determine, for example, if the majority of subjects increased, decreased or stayed the same at each visit. The baseline measurements will be examined to show where the subjects were before the study, in terms of their height and weight, compared to the population. Summary statistics will be calculated for the measurements and the changes in measurements at each visit by sex and overall. Depending on the distribution of the data, either a Wilcoxon signed rank test, or a one-sample t-test will be done to evaluate if the mean or median change from baseline is different from zero.

The number of subjects whose change increases, decreases, and stays the same will be tabulated at each visit. Due to the precise nature of the calculations, the “stays the same” category may be broadened to include changes other than zero, which are negligible (i.e. 0.5).

Z-scores for body weight and height and change from baseline in Z-scores for body weight and height will be summarized by visit. Figures for the median and IQR in height and weight Z-score by visit will be displayed.

In addition, summary statistics of the absolute value and change from baseline in both height and weight will be tabulated by visit.

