### **8.8. Other Analyses**

In general, all continuous endpoints will be summarized using an 8-number descriptive summary (n, mean, standard deviation, median, Q1, Q3, minimum, and maximum). All categorical endpoints will be summarized by the number and percent of subjects meeting the endpoint.

The proportion of subjects maintaining SVR, proportion of subjects with detectable HCV RNA due to re-emergence of pre-existing virus, proportion of subjects with detectable HCV resistance mutations, proportion of subjects with detectable HCV RNA due to re-infection, and the corresponding 95% confidence interval for each proportion will be computed by visit.

The proportion of subjects administered a Gilead OAV-containing regimen that maintain an SVR through end of study will also be estimated using a Kaplan-Meier model, allowing for censored observations due to early discontinuation from the Registry.

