### **8.9. Sample Size**

Due to the observational nature of this study, no formal power or sample size calculations were used.

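### The primary growth endpoint gets a test against zero change and no confidence interval, and on either scale that test does not answer the safety question

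*Protocol*

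**What the plan says.** Section 2 gives the primary objective: "To determine the long-term safety of anti-HCV regimens in the pediatric population as determined by assessments of growth and development". Section 8.2 lists the first primary safety endpoint as "Growth data by visit grouped by age and gender".

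Section 8.6.3.2 sets out the growth analysis. One paragraph deals with changes in body height and weight. It states "Summary statistics will be calculated for the measurements and the changes in measurements at each visit by sex and overall" and then plans a t-test or a signed rank test, whichever suits how the data turn out, to "evaluate if the mean or median change from baseline is different from zero". Two paragraphs later the Z-scores appear: "Z-scores for body weight and height and change from baseline in Z-scores for body weight and height will be summarized by visit". No test or interval is attached to that sentence.

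The default summary for continuous endpoints (synopsis and section 8.8) has eight numbers: n, mean, SD, median, quartiles, minimum and maximum. It contains no interval. For the virologic proportions, section 8.8 adds that "the corresponding 95% confidence interval for each proportion will be computed by visit". Section 8.9 records that "no formal power or sample size calculations were used".

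The statistical methods entry in the synopsis says that no hypothesis testing will be done, and section 8.6 calls the safety analyses descriptive. Section 8.10 leaves additional methods to the SAP.

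**The concern.** A safety objective asks how large a growth deficit the data can rule out. A test of zero change does not answer that. If it rejects, the p-value does not say whether the change is harmful. If it does not reject, the result says nothing about how large a fall remains possible, least of all in a cohort whose size was not planned. An interval answers the question directly, yet the protocol specifies intervals for the outputs that serve the secondary objectives and not for the primary endpoint.

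The scale makes this worse. The test sits with the raw measurements, where children are expected to grow, while the age- and sex-standardized Z-scores, the only scale on which zero means keeping pace with the reference population, are just summarized. The report could then show highly significant gains in height that say nothing about growth relative to peers. If the test is instead run on Z-scores, it could show non-significant changes in thin late-visit or by-sex rows that look more reassuring than they are.

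**Working it through.** **Inputs.** The protocol states no N, alpha, SD, effect size or margin for growth, so there is no planned figure to reproduce. Everything below is an assumption for illustration: two-sided alpha 0.05; SD of change in Z-score 0.6 (range 0.4 to 0.8); true mean fall 0.2 Z; n from 20 to 200. For raw height: mean gain 5 cm or 2 cm, SD of change 3 cm.

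**Formulas.** The one-sample t-test has n − 1 degrees of freedom and noncentrality (shift/SD) × √n. Power is the noncentral t probability beyond ± t(0.975, n − 1), and the chance of a non-significant result is 1 − power. The 95% interval half-width is t(0.975, n − 1) × SD/√n.

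**Reading 1: raw height, as the paragraph is written.**
- Gain 5 cm, n=10: noncentrality (5/3) × √10 = 5.27; power 99.6%.
- Gain 5 cm, n=20: noncentrality 7.45; power about 100%.
- Gain 2 cm: power 47% at n=10, 81% at n=20 and 99.6% at n=50.

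The usual result is a significant increase, whether or not the children are losing ground against the reference.

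**Reading 2: change in Z-score.** Worked case, n=20 and SD 0.6: noncentrality (0.2/0.6) × √20 = 1.49; critical value 2.093; power 29%; non-significant 71%. Half-width 2.093 × 0.6/√20 = 0.28.

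| n | Non-significant, SD 0.6 (SD 0.4 to 0.8) | 95% half-width, SD 0.6 (SD 0.4 to 0.8) |
|---|---|---|
| 20 | 71% (44 to 81%) | 0.28 (0.19 to 0.37) |
| 40 | 46% (13 to 66%) | 0.19 (0.13 to 0.26) |
| 100 | 9% (0.1 to 30%) | 0.12 (0.08 to 0.16) |
| 200 | 0.3% (under 0.1 to 6%) | 0.08 (0.06 to 0.11) |

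**What the interval adds.** Take an observed mean change of −0.1 Z with SD 0.6.
- n=20: p = 0.47; lower limit −0.1 − 0.28 = −0.38.
- n=40: p = 0.30; lower limit −0.1 − 0.19 = −0.29.

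Both tests are non-significant, yet the data still allow mean falls of roughly 0.3 to 0.4 Z. The p-value alone does not show this.

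**Consistency.** The synopsis excludes hypothesis testing; section 8.6.3.2 says a test will be done. Both cannot stand.

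**The case against.** Four points can be made for the plan.

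First, a reader might infer that the sponsor will treat a non-significant change as proof of safety. The documents do not support that. They set no such rule, margin or decision criterion, and they call the safety analysis descriptive. The risk is only that the result could be read that way.

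Second, a reader might infer that the zero null makes a reassuring result the default. On raw height and weight it does not, because growth usually makes the test significant. That argument applies only to a Z-score test, which section 8.6.3.2 does not specify. This narrows the point but does not rescue the test, which is uninformative about safety on the raw scale too.

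Third, the precision is not lost. Section 8.8 reports n, mean and SD, so a reader can rebuild a t-interval for the mean. Section 8.6.3.2 also plans figures of median and IQR Z-scores. This stands for the mean. It does not help for the median when the Wilcoxon test is used, and a primary result should not depend on readers computing it.

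Fourth, an interval column could be in the SAP, which is not shown, and the miss rates depend on small n. The registry is open to any centre with at least one eligible subject, so the whole cohort may be large, and at n=200 the problem nearly vanishes. Both are fair. However, the zero-null test is not deferred; the protocol commits to it. By-sex rows and late visits, with follow-up to Week 240 and discontinuations allowed, will also be smaller than the full cohort.

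**Conclusion.** The point holds in a limited form. The protocol fixes a poorly suited method for its primary growth endpoint: a test of zero change, on a scale it does not make clear, with no named interval, and in conflict with its own synopsis. On raw measurements the test mostly detects that children grow. On Z-scores its non-significance carries little information in small rows, and the weakness fades as n rises to 100 or 200. Those figures rest on an assumed 0.2 Z fall, an assumed SD and assumed sample sizes; none comes from the protocol. The missing interval alone would be a minor gap in presentation. It matters here because the stated test is the only inferential output that the protocol names for growth.

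**What to change.** In section 8.6.3.2, state that mean change from baseline in height and weight Z-score will be reported with a 95% confidence interval at each visit, with an interval for the median wherever medians are shown. State that growth safety will be interpreted from the lower limit, that is, the largest mean fall the interval still allows.

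Remove the zero-null test. If it is kept, confine it to Z-score change and say that a non-significant result is not evidence of no effect. Then reconcile the synopsis with section 8.6.3.2: removing the test settles the conflict, while keeping it means amending the synopsis.

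The cost is one sentence, one table column and, if the test stays, a small edit to the synopsis. No new data are needed.

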### **8.7. Quality of Life Analysis**

The data from PedsQL™ Pediatric Quality-of-life survey will be summarized with descriptive statistics at each visit by visit and age group and overall.

### **8.8. Other Analyses**

In general, all continuous endpoints will be summarized using an 8-number descriptive summary (n, mean, standard deviation, median, Q1, Q3, minimum, and maximum). All categorical endpoints will be summarized by the number and percent of subjects meeting the endpoint.

The proportion of subjects maintaining SVR, proportion of subjects with detectable HCV RNA due to re-emergence of pre-existing virus, proportion of subjects with detectable HCV resistance mutations, proportion of subjects with detectable HCV RNA due to re-infection, and the corresponding 95% confidence interval for each proportion will be computed by visit.

The proportion of subjects administered a Gilead OAV-containing regimen that maintain an SVR through end of study will also be estimated using a Kaplan-Meier model, allowing for censored observations due to early discontinuation from the Registry.

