Study Design:	
This Registry will enroll adolescent and pediatric subjects who received at least one Gilead HCV direct acting antiviral (DAA) while participating in Gilead-sponsored chronic hepatitis C clinical trials.
 
Once enrolled, subjects will be followed for up to 5 years. The Day 1 visit will be documented as the last visit of the previous Gilead-sponsored treatment protocol. Subsequent visits will occur at Weeks 24, 48, 72, 96, 144, 192, and 240. At each visit, subjects will have blood drawn for plasma HCV RNA quantification and viral sequencing (archive). In addition, a symptom-directed physical examination, body height and weight measurements, and Tanner Pubertal Stage Assessment (when appropriate) will be performed. A quality-of-life survey will be completed.
 
If a subject tests positive for HCV RNA after non-detectable levels at Day 1 or any time throughout the study, the subject will have a repeat blood sample drawn for confirmation. Subjects who begin a new treatment course for HCV infection will discontinue participation in the Registry.

Target Population:	Adolescent and pediatric subjects who received at least one Gilead HCV direct acting antiviral (DAA) while participating in a Gilead-sponsored chronic hepatitis C study.
Duration of Study Participation:	This observational Registry will follow subjects every 6 months for the first 2 years followed by every 12 months for up to five years.
Diagnosis and Main Eligibility Criteria:	
Inclusion Criteria:
 
To be eligible for participation, a subject must:
 

• Have previously participated in a Gilead-sponsored chronic hepatitis C study as an adolescent or pediatric subject and received at least one Gilead HCV direct acting antiviral (DAA);

• Parent or legal guardian able to provide written informed consent OR subject able to provide written informed consent and willing to comply with study requirements, as determined by IRB/IEC/local requirements and Investigator's discretion.

• Subject able to provide written assent, if they have the ability to read and write, as determined by IRB/IEC/local requirements and Investigator's discretion

 
Exclusion Criteria:
 

• Subject is currently receiving or plans to initiate a new course of hepatitis C therapy including any investigational drug or device during the course of the follow-up Registry.

---

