#### **3.2. Visit Schedule**

Once enrolled, subjects will be followed for up to 5 years. The subject and/or the subject's parent or legal guardian must provide written consent within 168 days from the last visit of the previous Gilead-sponsored treatment protocol. The Day 1 visit will be documented as the last visit of the previous Gilead-sponsored treatment protocol. Subsequent study visits will occur at Weeks 24, 48, 72, 96, 144, 192, and 240. At each subsequent visit, subjects will have blood drawn for plasma HCV RNA quantification and viral sequencing (archive). In addition, a symptom-directed physical examination, body height and weight measurements, and Tanner Pubertal Stage Assessment (when appropriate) will be performed. A quality-of-life survey will be completed. Reminder phone calls to subjects will be conducted by the site staff at 1-2 months prior to each study visit following the subject's Day 1 visit date.

While participating in the Registry, if a subject tests positive for HCV RNA after non-detectable levels at Day 1 (defined as HCV RNA  $\geq$  LLoQ) or any time throughout the study, they will be asked to return to the clinic for collection of a repeat blood sample for HCV RNA quantitation.

The assessments to be performed at each visit are described in Section 6.

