#### **3.3. Discontinuations**

While participating in the Registry, subjects will be discontinued for the following instances:

- Subjects who initiate a new course of hepatitis C therapy (including approved products and investigational agents);
- Subjects or parents/legal guardians who request to discontinue for any reason; it is important to clearly determine and document the specific reason for withdrawal of consent;
- Discontinuation of the Registry and/or subjects at the request of Gilead, regulatory agency or an Institutional Review Board (IRB)/Independent Ethics Committee (IEC).

If a subject meets withdrawal criteria or discontinues participation for any reason, the subject should complete an Early Termination visit.

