#### **6.3.2. Early Termination Visit**

Subjects discontinuing the Registry for any reason should undergo the following procedures:

- Perform symptom-directed physical examination
- Body height and weight measurements
- Tanner Pubertal Stage Assessment (if applicable)
- Complete quality-of-life survey
- Obtain blood samples for:
  - Plasma HCV RNA (If HCV RNA is detected after non-detectable levels at Day 1 or any time throughout the study, the subject will have a repeat blood sample drawn for confirmation)
  - Viral sequencing, (archive)
- Assessment of procedure-related AEs

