#### **8.4.1.2. Efficacy Analysis Set**

Efficacy Analysis Set is the same as safety analysis set.

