### **8.4.2. Data Handling Conventions**

Missing data can have an impact upon the interpretation of the trial data. In general, values for missing data will not be imputed.

All available data for subjects who do not complete the study will be included in data listings.

HCV RNA values below the LLoQ for the assay will be set to the lower limit minus 1 for calculation of summary statistics for the actual HCV RNA values and the change from baseline values by study visit. The reported values will be provided in the HCV RNA listing.

For selected analyses, HCV RNA data (IU/mL) will be transformed to the logarithmic (base 10) scale ( $\log_{10}$  IU/mL).

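### Durability of SVR can be overstated in Section 8.8, because retreatment forces exit from the Registry and the by-visit proportions and Kaplan-Meier censoring make no allowance for it

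*Protocol*

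**What the plan says.** **Exit rule.** Section 3.3 lists among those to be discontinued "Subjects who initiate a new course of hepatitis C therapy (including approved products and investigational agents". The synopsis (Study Design) says the same: "Subjects who begin a new treatment course for HCV infection will discontinue participation in the Registry". Section 5.2 repeats the rule.

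**By-visit proportions.** Section 8.8 names several proportions, including that of subjects maintaining SVR, and says the "corresponding 95% confidence interval for each proportion will be computed by visit". It gives no denominator. The only population on offer is all enrolled subjects, since "Efficacy Analysis Set is the same as safety analysis set" and the latter (Section 8.4.1.1) is everyone enrolled. On missing values, Section 8.4.2 says "In general, values for missing data will not be imputed".

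**Kaplan-Meier.** Section 8.8 also estimates maintenance of SVR to end of study by Kaplan-Meier, "allowing for censored observations due to early discontinuation from the Registry". The event and its date are not defined, and exit for retreatment is not separated from other exits.

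**Detection.** HCV RNA is measured at every visit (Section 6.3.1). After a positive result in a subject who had been undetectable, "they will be asked to return to the clinic for collection of a repeat blood sample for HCV RNA quantitation" (Section 3.2). Section 6.3.2 adds: "Subjects discontinuing the Registry for any reason should undergo the following procedures", and the list includes plasma HCV RNA. Its timing relative to the start of new therapy is not given.

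**The concern.** A subject who holds SVR has little reason to start HCV therapy unless virus has come back. The exit rule therefore removes mainly failures, and the analysis has to allow for that. As written, it does not clearly do so in either estimate.

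For the by-visit proportions, take a subject with confirmed loss at Week 48 who is retreated. There is no Week 72 sample. With no imputation, and proportions formed from subjects with data at the visit, this failure counts once and is then absent from Weeks 72 to 240.

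For the Kaplan-Meier, the difficulty is narrower. It concerns a subject whose relapse is found outside the Registry and who starts therapy before any Registry sample shows it. Visits are 48 weeks apart after Week 96, so there is room for this. Section 3.3 makes the start of therapy the withdrawal criterion and then asks for the Early Termination visit, so that sample may be drawn after therapy has begun. Such a subject would be censored as if still in SVR.

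Both effects raise apparent durability, and Section 1.2 names durability as a purpose of the Registry.

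**Working it through.** **Inputs from the protocol.** Seven follow-up visits: Weeks 24, 48, 72, 96, 144, 192 and 240 (Section 3.2). Section 8.9 reports no sample size calculation and no durability figure is stated, so there is nothing of the plan's own to reproduce.

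**Assumptions, none given in the protocol.** 100 subjects with SVR at entry; *L* of them lose it (2, 5 or 10), spread evenly over the seven visits; no other dropout. Let *r* be the share of losers retreated and gone before their next visit, and *f* the share retreated before any Registry sample shows the loss. The true proportion still in SVR at Week 240 is (100 − *L*)/100.

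**Step 1: by-visit proportion on observed cases, all losses detected (*f* = 0).** At Week 240 the numerator is 100 − *L*. Losses at the first six visits total 6*L*/7, and a share *r* of them is missing from the denominator:

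P = (100 − L) / (100 − 6Lr/7)

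For *L* = 5 and *r* = 1: 95 / (100 − 4.286) = 95 / 95.714 = 99.25%.

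| Losses per 100 | True | r = 0 | r = 0.5 | r = 1 |
|---|---|---|---|---|
| 2 | 98% | 98.00% | 98.85% | 99.71% |
| 5 | 95% | 95.00% | 97.08% | 99.25% |
| 10 | 90% | 90.00% | 94.03% | 98.44% |

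The direction does not depend on the assumed rate. If anyone who lost SVR is retreated and leaves, later figures are too high; if no one is, they are right.

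**Step 2: Kaplan-Meier, every loss detected before exit (*f* = 0).** With n_j subjects at risk at visit *j*, the factor is 1 − (L/7)/n_j = n_(j+1)/n_j. The product over seven visits telescopes to (100 − L)/100, which gives 98%, 95% and 90%. There is no bias, whether or not these subjects are later retreated.

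**Step 3: Kaplan-Meier, a share *f* of losses censored.** Just before each visit, fL/7 subjects leave as censored, so the factor is

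1 − (1 − f)(L/7) / (n_j − fL/7)

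For *L* = 5 and *f* = 0.5, the first factor is 1 − 0.357/99.643 = 0.99642, the seventh is 1 − 0.357/95.357 = 0.99625, and the product of all seven is 97.46%.

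| Losses per 100 | True | f = 0 | f = 0.25 | f = 0.5 | f = 1 |
|---|---|---|---|---|---|
| 2 | 98% | 98.00% | 98.50% | 98.99% | 100% |
| 5 | 95% | 95.00% | 96.22% | 97.46% | 100% |
| 10 | 90% | 90.00% | 92.39% | 94.85% | 100% |

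**Step 4: after the fix.** Carrying losses forward restores 100 as the Step 1 denominator. Counting undocumented retreatment as an event removes the censoring in Step 3. Under these assumptions both estimates return the true 98%, 95% and 90%, apart from small differences in event timing.

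**The case against.** A fair opponent has four arguments.

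*The Kaplan-Meier already handles relapse.* HCV RNA is taken at every visit and a positive result is repeated, so a detected loss is an event before retreatment removes the subject. This stands, and Step 2 confirms it. A reader might infer that the Kaplan-Meier censors everyone who relapses and is retreated; the protocol does not say that, and nothing in it lets a later discontinuation cancel an earlier event. What survives is the subject retreated before detection. The protocol leaves that route open but gives no sign of how often it is taken.

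*The by-visit denominator is inferred.* True. Observed cases is the natural reading of Sections 8.4.2 and 8.8 together, but it is not stated, and maintaining SVR could be read as a cumulative status. The other literal reading, all enrolled subjects, does not measure durability either: the Registry also follows subjects who never achieved SVR, and they have nothing to maintain.

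*These are details for the SAP.* Denominators and event dates often are, and an SAP not shown here may settle them. But the protocol itself fixes the exit rule, the general absence of imputation and the censoring of early discontinuation. Their combination causes the problem, and Section 8.10 leaves only additional methods to the SAP.

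*The endpoint is minor.* The primary endpoints are growth and pubertal development (Section 8.2), and the Registry is descriptive. This lowers the severity but does not remove the point.

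**Conclusion.** The point holds in a conditional form: durability of SVR *can* be overstated. That it *is* overstated cannot be shown, because the protocol gives no rate of loss, of retreatment, or of retreatment before detection.

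The by-visit proportions are the stronger part. On an observed-case reading, the overstatement at Week 240 runs from nil (no one retreated) to 1.7, 4.3 and 8.4 percentage points for 2, 5 and 10 losses per 100, all retreated before the next visit. The Kaplan-Meier is sound for losses detected in the Registry. It errs only for subjects retreated before detection: by 2.5 points, for example, if half of 5 losses per 100 go that way.

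Severity is moderate to low. No primary conclusion depends on this, but any bias runs in favour of the product on a stated purpose of the Registry, and wording alone corrects it.

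**What to change.** In Section 8.8, or in the SAP with a reference from 8.8:

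1. Base the proportions maintaining SVR on subjects with SVR at Registry entry. Keep a subject with confirmed loss in the denominator as not maintained at all later visits.
2. Define the Kaplan-Meier event as confirmed loss of SVR, dated at the first HCV RNA sample that is later confirmed.
3. If a subject with SVR starts new HCV therapy without a documented event before it, count the start of therapy as an event rather than censoring it.
4. Censor all other exits at the last HCV RNA sample.
5. Add a sensitivity analysis that censors retreatment, so that the two versions show the range.

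The cost is wording and programming; no visit, sample or treatment rule changes. There are two small downsides. Therapy started for another reason counts as a loss in the main analysis, which item 5 makes visible. And if many subjects leave for unrelated reasons, retained losses are set against a shrinking number of others, so the by-visit figure may lean low; it should be read beside the Kaplan-Meier estimate, which allows for such exits.
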